- 4.To evaluate predictors of mortality. Factors that will be evaluated include: sex, age, comorbidities (dementia, diabetes, CAD), laboratory values including leukocytosis prior to procedure, blood/urine culture, albumin).

Please save frequently

c) Describe the study design (e.g., single/double blind, parallel, crossover, control, experimental, observational, etc.). If the study is investigator-initiated, a timeline for individual subject recruitment, follow-up, and analysis for the study is required. Also, indicate if the subjects will be randomized.

This study is a retrospective chart review. We are unsure of the number of patients, but will estimate approximately 150 patients total, with 75 patients with PEG placed before 7 days since acute dysphagic stroke and 75 patients with PEG placed after 7 days for acute dysplagic stroke. Should our search criteria yield fewer or more patients than expected, then we will simply report the total number of patients that fit our inclusion and exclusion criteria. Patients will be enrolled from St. Louis University Hospital (SLU) along with other SSM hospitals. We will use data from our medical record system, Epic, and also the gastroenterology procedure

Protocol Title:

Percutaneous Endoscopic Gastrostomy (PEG) tube placed less than or greater than 7 days post stroke: Mortality, Predictors of Mortality, Complications, and Outcomes.

.-----

documentation program ProVation. We will include patients from 2011-2014 who underwent PEG tube placement post acute dysphagic stroke. Patients will be included in the study by evaluating International Classification of Diseases (ICD) codes associated with each patient's admission as well as ProVation biling diagnosis of PEG tube placement. ICD is a healthcare classification system, providing a system of diagnostic codes for classifying diseases.

PEG tubes were placed endoscopically using the standard "pull through" technique described by Ponsky and Gauderer.7 We will not be including PEG tubes placed surgically or radiologically. All patients were admitted to the hospital at the time of the PEG insertion and were post acute dysphagic stroke. A dose of antibiotics, most times, Ancef 1 gm IV 30 minutes prior to the procedure was given. However, other antibiotics with similar spectrum of coverage may have been used. The PEG site was examined for infection and bleeding 24 hours after insertion and tube feeds were subsequently recommended at that time.

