Percutaneous Endoscopic Gastrostomy (PEG) tube placed less than or greater than 7 days post stroke: Mortality, Predictors of Mortality, Complications, and Outcomes.

classification system, providing a system of diagnostic codes for classifying diseases.

PEG tubes were placed endoscopically using the standard "pull through" technique described by Ponsky and Gauderer.7 We will not be including PEG tubes placed surgically or radiologically. All patients were admitted to the hospital at the time of the PEG insertion and were post acute dysphagic stroke. A dose of antibiotics, most times, Ancef 1 gm IV 30 minutes prior to the procedure was given. However, other antibiotics with similar spectrum of coverage may have been used. The PEG site was examined for infection and bleeding 24 hours after insertion and tube feeds were subsequently recommended at that time.

c) If the proposed study is a clinical trial where a drug, vaccine, device or other treatment is compared to a placebo group or comparison treatment group, what are the guidelines or endpoints by which early decisions regarding efficacy or lack of efficacy can be made? For example, it may be reasonable to stop enrollment on a study when efficacy has already been clearly demonstrated, to avoid unnecessary enrollments of additional subjects. Alternatively, it may be reasonable to stop enrollment when it is clear that efficacy will never be demonstrated, given the statistical power of the study as designed. Describe the guidelines that are in place to assist in making these determinations, if relevant to the proposed study.

N/A

d) Describe how data analysis will be performed (statistical tests, methods of evaluating data) and indicate the smallest group/unit for which separate reporting will occur. For studies involving a questionnaire, if data and reliability information are available, please describe or provide references. For full board, unfunded studies describe sample size determination and power analysis. If none, please justify.

Sample size calculation for this particular study is not feasible. This is a single center study and we are limited to the number of patients who have received PEG tubes at this institution and we cannot create a large sample size. Thus, no sample size calculation is needed. All patient's who fit the inclusion criteria will be included in this study.

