5. SSMSL

All research involving SSMSL locations (including Cardinal Glennon), including inpatient or outpatient services and medical record access, requires approval from the SSM STL or SSM Cardinal Glennon Research Business Review (RBR) prior to study initiation. This process is designed to facilitate compliance with state and federal regulations as they pertain to research in hospitals and clinical research billing. While researchers can begin to complete the SSM RBR form at any time, the form should not be submitted until the IRB and the CTO have approved the study. Please contact the SSMSL Office at [name] or [name]. [contact] for more information.

Not Applicable

- X Yes, study requires RBR review
- Does this project require registration on ClinicalTrials.gov, and/or is this project subject to the NIH GCP Training Requirement? (Select "Yes" if either apply)

Registration may be required if any of the following apply: 1) The project meets the FDAAA definition of an "Applicable Clinical Trial", which requires registration on ClinicalTrials.gov. 2) As of January 1, 2017, a new NIH policy mandated biomedical and behavioral "Clinical Trials" to be registered on ClinicalTrials.gov. In addition, NIH policies require personnel on NIH "Clinical Trials" to take GCP training every three years. 3) Registering may be required for Journal Publication (ICMJE). Please review relevant definitions here. Contact the CTO at [contact] with questions about registering on ClinicalTrials.gov and refer to the training page of the IRB website for

Ν

Protocol # 29062 [name]

	CC		

Percutaneous Endoscopic Gastrostomy (PEG) tube placed less than or greater than 7 days post stroke: Mortality, Predictors of Mortality, Complications, and Outcomes.

information on NIH GCP Training requirements.

* * * Subject Population * * *

- 8. Subject Population In the space below, please detail the participants that you are requesting to recruit (include description of each group requested)
- a) Expected age range of subjects. (For example ≥ 18 yrs to 90 yrs).

≥18 years old

b) Number of evaluable subjects to be accrued at SLU or SLU site (this includes all sites under the direction of the SLU PI).

150 patients, 75 patients with PEG placed less than 7 days post stroke and 75 patients with PEG placed greater than or equal to 7 days post stroke

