Exceeding the number listed here is a protocol violation. Prior IRB approval is required if additional participants are to be accrued. If applicable, this number should be consistent with your power analysis described in 3d.

c) Number of evaluable subjects to be accrued study wide. *?HELP?*

150 patients,75 patients with PEG placed less than 7 days post stroke and 75 patients with PEG placed greater than or equal to 7 days post stroke

d) If including vulnerable populations (minors, pregnant women and fetuses, neonates, non-English speaking, economically or educationally disadvantaged, prisoners, adults temporarily or permanently unable to consent for themselves): 1) provide the rationale for the importance of including this population in the research, and 2) specify the measures being taken to minimize risks to potentially vulnerable subjects. Click on hyperlinks to access SLU Guidelines containing additional considerations and strategies for mitigating risks.

N/A

Protocol # 29062 [name]

Protocol Title:

Percutaneous Endoscopic Gastrostomy (PEG) tube placed less than or greater than 7 days post stroke: Mortality, Predictors of Mortality, Complications, and Outcomes.

e) If women, minorities, or minors are not included, a clear compelling rationale must be provided unless not applicable. Examples for not including minors: disease does not occur in children; drug or device would interfere with normal growth and development; etc. If federally funded reference appropriate section of the sponsors protocol/grant. *?HELP?*

Minors are not included in the study as acute dysphagic stroke is rarely seen in minors.

- f) If any specifically targeted subjects are students, employees, or laboratory personnel, specify the measures being taken to minimize the risks and the chance of harm to these potentially vulnerable subjects. See SLU Guidelines for additional considerations and strategies for mitigating risks.

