Percutaneous Endoscopic Gastrostomy (PEG) tube placed less than or greater than 7 days post stroke: Mortality, Predictors of Mortality, Complications, and Outcomes

HIPAA Documents

Waiver of Authorization

NOTE: Investigators seeking a waiver of authorization must provide justification to all items. Simply restating the criteria in the response box is not acceptable; responses must include a justification as to how/why the study meets each criterion.

a) Please provide a brief description of the protected health information for which use or access has been determined to be necessary.

The research team will compile data from SLU Hospital's medical record systems EPIC and Provations. The data will include either patient's name or MRN number, dates, medical history, labs, procedure details. There will be no direct patient contact, this is a retrospective chart review. Patient identifying information will be coded. One master key will be stored on a password protected computer until the manuscript is accepted.

b) To obtain approval for a waiver or alteration of HIPAA authorization for the use and/or disclosure of PHI resulting from participation in a research study, the project has to meet the criteria listed below. Please explain how your study meets these criteria.

Protocol # 29062 [name]

Protocol Title:

Percutaneous Endoscopic Gastrostomy (PEG) tube placed less than or greater than 7 days post stroke: Mortality, Predictors of Mortality, Complications, and Outcomes.

 The use or disclosure of PHI involves no more than minimal risks to the privacy of individuals.

The only risk is loss of confidentiality. The data will be coded and stored on a password protected computer.

2) PHI information will not be reused or disclosed to any other person or entity, except as required by law for authorized oversight of the research study, or for other research for which the use or disclosure of PHI would be permitted by HIPAA.

Correct. The PHI will not be shared with anyone outside of the research team. It will only be shared by IRB and if required by law.

3) The research could not practicably be conducted without the waiver.

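### The protocol conflicts with itself on which patients enter the cohort (all eligible, or no more than 150 without IRB approval) and on which hospitals supply them (one center, or SLU plus other SSM hospitals)

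*Protocol*

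**What the plan says.** **Cohort size.** Sections 2c and 3b give the size as a guess: "We are unsure of the number of patients, but will estimate approximately 150 patients total". They then say what happens if the guess is off: "Should our search criteria yield fewer or more patients than expected, then we will simply report the total number of patients" meeting the criteria. Section 3d is categorical: "All patient's who fit the inclusion criteria will be included in this study". The justifications for the waiver of consent (section 13) and the waiver of authorization (section 15) repeat that all qualifying patients are needed.

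Item 8b enters "150 patients, 75 patients with PEG placed less than 7 days post stroke and 75 patients with PEG placed" at 7 days or later. Item 8c enters the same figures study wide. Neither carries the word for an estimate that 2c and 3b use. The form text under 8b then states: "Exceeding the number listed here is a protocol violation". The next sentence of the form requires IRB approval beforehand if more are to be accrued.

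**Sites.** Section 3d declines a sample size calculation on this ground: "This is a single center study and we are limited to the number of patients who have received PEG tubes at this institution". Item 3a, which asks both about multicenter projects and about research at multiple sites, is answered N. The waiver of authorization in section 15 names one source: "The research team will compile data from SLU Hospital's medical record systems EPIC and Provations". Sections 2c and 3b say otherwise: "Patients will be enrolled from St. Louis University Hospital (SLU) along with other SSM hospitals". In section 7, the review required for SSM locations is ticked as applicable.

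**The concern.** In a retrospective chart review, the rule for who enters is the main design decision. Two parts of that rule are stated in ways that cannot all be followed.

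On size, an abstractor who finds the 151st eligible chart gets different instructions from different sections. Under 3d it goes in. Under 8b it may not go in until the IRB has agreed. Nothing says which rule prevails or that approval will be sought, and no rule says which charts would count toward 150 if the number were held. Anyone choosing charts at that stage would be working from records that also hold the date of death (item 8g), so an improvised choice could be related to the outcome.

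On sites, the single-center statement is more than a description. It is the reason given for having no sample size calculation. If other SSM hospitals contribute, that reason is wrong as written, and the section 15 account of data sources does not match the cohort. The planned primary comparison in 3d is also a pooled log-rank test. If hospitals differ both in how early they place PEG tubes and in mortality, pooling would attribute some of the hospital difference to timing.

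**Working it through.** **The plan's own figure.** 75 + 75 = 150, so the number in 8b and 8c adds up. The protocol gives no effect size, power or event rate behind it, so there is nothing further to reproduce. The equal totals in 8b and 8c are not an error, because 8b counts all sites under the SLU investigator.

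**Size rules side by side.**

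| Yield of the search | 2c, 3b, 3d | 8b, 8c and form text | Conflict? |
|---|---|---|---|
| Below 150, any split | Report what is found | Nothing exceeded | No |
| Exactly 150, split not 75/75 | Report what is found | Total not exceeded; group figures differ from those listed | No breach |
| Above 150, IRB approval obtained first | Include all | Permitted | No, but 2c/3b mention no such step |
| Above 150, no prior approval | Include all | Protocol violation | Yes |

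The collision is therefore confined to the last row.

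**How likely is a yield above 150?** The documents give no count, so this is an illustration. Assume that the eligible count is Poisson with mean m, and compute P(N > 150):

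- m = 120: 0.004
- m = 135: 0.093
- m = 150: 0.478
- m = 165: 0.871
- m = 180: 0.988

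If the estimate of 150 is about right, the chance of going over is close to one half. An error of 15 patients in the estimate moves it to 9% or 87%.

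**Is 75/75 a realistic outcome?** Assume that 150 patients are each equally likely to fall in either group. Then P(75/75) = C(150, 75) × 0.5^150 = 0.065. With all eligible charts included, an exact even split would be a coincidence, so 75/75 can only be an expectation.

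**Site statements side by side.**

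- One institution: 3d (single center), 3a (N), the expedited-review justification and section 15 item a (SLU Hospital's records).
- More than one: 2c and 3b (SLU Hospital and other SSM hospitals), section 7 item 5 (SSM review ticked).

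The second half of the 3a question covers research at multiple sites, so the N cannot be explained by the absence of a second investigator.

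**What pooling could do (assumed rates, illustration only).** Take two hospitals of equal size and no effect of timing. Hospital A places 70% early with 15% mortality; hospital B places 30% early with 30% mortality. The early group is then 70% from A and 30% from B, and the late group is the reverse.

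- Early: 0.7 × 0.15 + 0.3 × 0.30 = 0.195
- Late: 0.3 × 0.15 + 0.7 × 0.30 = 0.255

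The crude gap is 25.5% − 19.5% = 6.0 percentage points, although within each hospital the two groups have the same mortality. A test stratified by hospital compares patients within hospitals and so removes this gap.

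**The case against.** The strongest reply is that the investigator's intention is clear and the conflict is clerical. Every statement in the study's own words points to including all eligible patients. The 150 in 8b and 8c is the same estimate typed into a field that wants a number, and the violation sentence is standing form text. This is a fair account of how the mismatch arose. It does not remove the mismatch, because the form text governs whatever number is entered, and 2c and 3b mention no approval step.

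Four stronger readings are tempting, and the documents do not support them.

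- A reader might infer that a yield above 150 forces either a violation or the dropping of charts. It does not: the form's next sentence allows more patients with prior IRB approval, and no section says that charts will be dropped.
- A reader might infer that any split other than 75/75 is a breach. Only exceeding the listed number is.
- A reader might infer that hospital practice drives both timing and mortality here. The documents say nothing about how hospitals differ or how many patients each would supply.
- A reader might infer that correcting the single-center statement makes a power calculation due. The form asks for one in full-board, unfunded studies, and this study requests expedited review. What fails is the reason given, not the absence of the calculation.

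It can also be said that stratification factors are often left to an analysis plan, and that 3d allows additional analyses. That stands, so stratification is offered here as a conditional improvement. Which hospitals contribute is another matter: it defines the population, and the protocol already fixes it in two ways.

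**Conclusion.** The concern holds as an internal contradiction on two points that determine who is in the cohort, and it should be corrected.

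On size, the conflict arises only when the search yields more than 150 patients and approval has not been obtained first. Under a Poisson assumption, the chance of a yield above 150 runs from 9% to 87% as the true mean goes from 135 to 165. The protocol's own uncertainty about the number makes this a live possibility.

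On sites, the contradiction is present whatever the yield. It undercuts the stated reason for having no sample size calculation and leaves the section 15 description out of step with 2c and 3b.

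No bias has been demonstrated. Selection through truncation is a risk only if someone enforces the cap by leaving charts out, which the plan does not propose. The 6.0-point hospital gap rests entirely on assumed rates. It shows that pooling could mislead if hospitals differ, not that it does here.

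**What to change.** 1. Run a count query of eligible 2011-2014 charts. Enter in 8b and 8c a ceiling at or above that count, or obtain IRB approval before going beyond 150 and say so in 2c and 3b.
2. Mark 75/75 as an expectation only, and state that all eligible charts are included with no truncation in either group.
3. Give one list of participating hospitals and use it in 2c, 3a, 3b, 3d and section 15, with the expedited-review justification brought into line. If SSM hospitals contribute, correct the single-center statement in 3d and reword the reason for having no sample size calculation. If they do not, remove them from 2c and 3b and revisit the section 7 tick.
4. If more than one hospital contributes, record the hospital for each patient and stratify the planned log-rank test by it. The data list in item 8g does not name the hospital; the data collection sheet is attached but not shown, so check it.

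The cost is one IRB amendment and one count query. Stratification needs one extra field and loses a little information if a hospital has few patients.

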15. HIPAA

Studies that access, receive or collect protected health information (PHI) are subject to HIPAA regulations. PHI is health information with one or more personal identifiers. For more information visit the IRB HIPAA page or refer to the SLU IRB HIPAA Guidance.

1. Will health information be accessed, received or collected?

No health information. HIPAA does not apply.

X Yes (continue to question 2).

2. Which personal identifiers will be received or collected/recorded?

No identifiers. I certify that no identifiers from the list below will be received or collected and linked to health information. (Skip remainder of page).

Limited identifiers will be received or collected/recorded (study will likely require a data use agreement). Select Data Use Agreement- INTERNAL or Data Use Agreement- EXTERNAL as appropriate, below.

City/State/Zip codes

Person-specific dates (e.g., date of birth, dates of service, admission/discharge dates, etc.)

Age (if subjects are 90+ years)

At least one direct identifier will be received or collected/recorded.

X Names

Social Security numbers

Telephone numbers

Linkable code or any other unique identifying number (note this does not mean the unique code assigned by the Investigator(s) to code the research data)

All geographic subdivisions smaller than a State, including street address, city, county, precinct, zip code, and their equivalent geocodes, except for the initial three digits of a zip code, if, according to the current publicly available data from the Bureau of the Census: (1) The geographic unit formed by combining all zip codes with the same three initial digits contains more than 20,000 people; and (2) The initial three digits of a zip code for all such

Protocol # 29062 [name]

Protocol Title:

Percutaneous Endoscopic Gastrostomy (PEG) tube placed less than or greater than 7 days post stroke: Mortality, Predictors of Mortality, Complications, and Outcomes.

...........

geographic units containing 20,000 or fewer people is changed to 000

X All elements of dates (except year) for dates directly related to an individual, including birth date, admission date, discharge date, date of death; and all ages over 89 and all elements of dates (including year) indicative of such age, except that such ages and elements may be aggregated into a single category of age 90 or older

Fax numbers

Electronic mail addresses

X Medical record numbers

Health plan beneficiary numbers

Account numbers

Certificate/license numbers

Vehicle identifiers and serial numbers, including license plate numbers

Device identifiers and serial numbers

Web Universal Resource Locations (URLs)

Internet Protocol (IP) address numbers

Biometric identifiers, including finger and voice prints

Full face photographic images and any comparable images

If you are receiving or collecting/recording health information and at least one personal identifier, please continue to complete the sections, below.

3. Sources of Protected Health Information:

- X Hospital/medical records for in or out patients
- X Physician/clinic records
- X Laboratory, pathology and/or radiology results

Biological samples

Interviews or questionnaires/health histories

Mental health records

- X Data previously collected for research purposes
- X Billing records
- X Other

Please describe:

Procedure records

- 4. If data will be shared outside the research team and the study involves PHI indicate how the research team will share the information.
 - X Not applicable (continue to question 5).

Only linkable code that can link data to the identity of the subject. A code access agreement or business associate agreement may be needed when data are shared with other non-SLU entities. If necessary, the agreement can be added and uploaded in item #5, below.

Limited identifiers: Zip codes, dates of birth, or other dates only. The study qualifies as a Limited

Protocol # 29062 [name]

Protocol Title:

Percutaneous Endoscopic Gastrostomy (PEG) tube placed less than or greater than 7 days post stroke: Mortality, Predictors of Mortality, Complications, and Outcomes.

Data Set. A data use agreement may be needed when data are shared with other non-SLU entities. If necessary, the agreement can be added and uploaded in item #5, below, using DUA-external option.

With unlimited identifiers. The consent document and HIPAA Authorization form must describe how the information will be disclosed.

5. HIPAA Documentation is required for this study. Use the table below to add HIPAA Documents for your study.

HIPAA Documents

HIPAA Documents	Title	Attached Date
Waiver of Authorization	Percutaneous Endoscopic Gastrostomy (PEG) tube placed less than or greater than 7 days post stroke: Mortality, Predictors of Mortality, Complications, and Outcomes	01/24/2018

Title

Percutaneous Endoscopic Gastrostomy (PEG) tube placed less than or greater than 7 days post stroke: Mortality, Predictors of Mortality, Complications, and Outcomes

HIPAA Documents

Waiver of Authorization

NOTE: Investigators seeking a waiver of authorization must provide justification to all items. Simply restating the criteria in the response box is not acceptable; responses must include a justification as to how/why the study meets each criterion.

a) Please provide a brief description of the protected health information for which use or access has been determined to be necessary.

The research team will compile data from SLU Hospital's medical record systems EPIC and Provations. The data will include either patient's name or MRN number, dates, medical history, labs, procedure details. There will be no direct patient contact, this is a retrospective chart review. Patient identifying information will be coded. One master key will be stored on a password protected computer until the manuscript is accepted.

b) To obtain approval for a waiver or alteration of HIPAA authorization for the use and/or disclosure of PHI resulting from participation in a research study, the project has to meet the criteria listed below. Please explain how your study meets these criteria.

Protocol # 29062 [name]

Protocol Title:

Percutaneous Endoscopic Gastrostomy (PEG) tube placed less than or greater than 7 days post stroke: Mortality, Predictors of Mortality, Complications, and Outcomes.

 The use or disclosure of PHI involves no more than minimal risks to the privacy of individuals.

The only risk is loss of confidentiality. The data will be coded and stored on a password protected computer.

2) PHI information will not be reused or disclosed to any other person or entity, except as required by law for authorized oversight of the research study, or for other research for which the use or disclosure of PHI would be permitted by HIPAA.

Correct. The PHI will not be shared with anyone outside of the research team. It will only be shared by IRB and if required by law.

3) The research could not practicably be conducted without the waiver.

Once the PEG tube is placed, patients are not seen or evaluated by gastroenterology after this admission. I do not have regular contact with this patient population. Due to the fact that post dysphagic stroke PEG tubes are a very specific criteria for inclusion, we will need all patients who fit this criteria included in this study. Previous studies have had small sample sizes and we hope have include as many patients that fit our criteria as possible to improve the power of our study.

- 4) The research could not practicably be conducted without access to and use of PHI.

 Correct. It is necessary to use PHI to open patient's chart and evaluate data as well as initially organize data.
- c) Please describe an adequate plan to protect any identifiers from improper use and disclosure.

 The PHI will be kept on a password protected computer, patient information will be coded with only one master key. This information will only be accessed only by the research team.
- d) Please describe an adequate plan to destroy the identifiers at the earliest opportunity consistent with conduct of the research, unless there is a health or research justification for retaining the identifiers or such retention is otherwise required by law.

The code will be destroyed after the manuscript has been submitted. After the code is destroyed, there is no more PHI is present.

* * * Attachments * * *

16. Attachments

In this section, please upload additional documents associated with your protocol. Failure to attach files associated with the protocol may result in the protocol being returned to you.

Possible documents for this protocol could include:

Bibliography

Protocol # 29062 [name]

Protocol Title:

Percutaneous Endoscopic Gastrostomy (PEG) tube placed less than or greater than 7 days post stroke: Mortality, Predictors of Mortality, Complications, and Outcomes.

- Cooperating Institution's IRB Approval
- Data Collection Sheet
- Debriefing Script
- Device Information/Documentation
- Grant Proposal/Sub-Contract
- Human Subjects Training Certificate/Proof of Training
- Information Sheet/Brochure
- Interview/Focus Group Questions
- · Investigator's Brochure
- Letter of Agreement/Cooperation
- IND Application Letter
- Package Insert
- Patient Diary Form
- Questionnaire/Survey
- Recruitment Material (e.g., flyers, ads, e-mail text)
- Safety Information (DSM Information)
- Scientific/PPC Review or Department Chair Review
- Sponsor's Protocol
- Sponsor's Protocol Amendment
- Study Design Chart/Table
- Other files associated with the protocol (most standard formats accepted: pdf, jpg, tiff, mp3, wmv, etc.)

To update or revise any attachments, please delete the existing attachment and upload the revised document to replace it.

Document Type	Document Name	Attached Date	Submitted Date
Scientific/PPC Review or Department Chair Review		01/30/2018	02/01/2018
Data Collection Sheet	Approved_PEG Data Collection Sheet	02/19/2018	02/19/2018

Document Type Scientific/PPC Review or Department Chair Review

